Renal scarring in childhood, whether acquired or congenital, is associated with hypertension, preeclampsia, and renal failure later in life.^{2-4, 20} As numerous experimental and longitudinal studies have shown, UTIs cause permanent and significant renal scarring.^{17, 18, 21-27} Furthermore, there is a clear dose-response relationship between the number of UTIs and progression of scarring.²⁸⁻³¹ On the other hand, it is also clear, especially when one looks at referral populations with a large proportion of children with high-grade VUR, that some children are born with small poorly-functioning kidneys. The clinical and radiological presentations of congenital and acquired scarring, albeit overlapping, are often distinct. Dysplasia, which is often detected prenatally,³² is most frequently seen in males with grades IV or V VUR and is characterized by globally atrophied kidney(s) with little or no function.³³⁻³⁶ In contrast, children with UTI-related scarring are most often females who present later in childhood with focal scars.^{3, 22, 37}

Studies have shown that both UTI and dysplasia contribute to ESRD. In her 10 to 41 year follow-up of 226 children with VUR, Smellie noted that those with poor prognosis fell into two categories: boys with severe VUR and scarring at presentation, and girls with mild to moderate VUR with scarring secondary to recurrent

UTIs.³⁸ The studies by Merrick and Wennerstrom show the same pattern, with both dysplasia and UTI contributing to ESRD.^{20, 29, 39}

By examining the outcome of studies that included mostly children likely to have had acquired renal scarring (and not dysplasia) – i.e., studies of females with low-grade VUR or no VUR – one can get a better appreciation for the morbidity associated with childhood UTI. Jacobson reported on a 27-year follow-up of 30 patients (87% females) with non-obstructive focal scarring following APN in childhood.^{4, 40} Approximately 10% of patients developed end-stage renal disease, 23% developed hypertension, and 13% of women experienced preeclampsia. Raz followed 63 adult women hospitalized with uncomplicated APN for 10-20 years; 8% had evidence of impaired renal function (GFR<75 mL/min per 1.73 m²).⁴¹ In a 37-year follow-up study, of 267 children (89% female) with VUR, 9% developed ESRD.⁴² In a long-term study of 100 adults (83% female) with reflux nephropathy, 22 of the 23 kidneys removed showed no histological signs of dysplasia.⁴³

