Recent longitudinal UTI studies that were conducted in primary care settings have found that 0% to 2% of children had evidence consistent with dysplasia at enrollment (see preliminary data).⁴⁴⁻⁴⁶ Yet, in these same studies, approximately 15% of children developed permanent renal scarring.^{44, 46}

In summary, there is overwhelming evidence to support the role of APN in the development of permanent renal injury in children. Recent studies confirm the notion that earlier studies likely overestimated the importance of acquired scarring, but that APN remains an important and preventable cause of permanent renal injury.²²

[figure not shown]
II. Inflammation Leads to Renal Scarring (Figure 1)

APN occurs when bacteria successfully ascend from the bladder to the kidney. Approximately two-thirds of young children with febrile UTI have evidence of renal parenchymal involvement.^{8, 12, 22} VUR, dysfunctional elimination syndrome (DES),^{47, 48, 49-52} and a delay in treatment all predispose to APN. In the kidney, the bacterial inoculum triggers a chemokine response that recruits neutrophils from the blood stream. This intense neutrophilic response results in the accumulation of oxygen radicals and lysosomal enzymes, which, in some individuals, leads to irreversible renal injury. Through a series of animal experiments, Bille,⁵³ Roberts,⁵⁴ and Glauser,¹³ assessed the role of neutrophil response in the pathogenesis of renal injury. Reduction in neutrophil activity through the use of superoxide dismutase,⁵⁴ cyclophosphamide,¹³ or colchicine¹³ was associated with decreased scarring in rats or monkeys with experimentally induced APN. These results were striking because even though animals treated with these agents had higher bacterial counts in their kidneys, reduction of the inflammatory response was associated with less renal damage. The authors concluded that the inflammatory response, rather than direct damage from the bacterial infection, is the most important factor in the formation of renal scars.

III. Treatment of VUR is not Sufficient to Reduce Renal Scarring

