The centers participating in this study are: Children's Hospital of Pittsburgh, Nationwide Children's Hospital in Columbus, the American Family Children's Hospital which is a children's hospital within the University of Wisconsin system, Children's National Medical Center in Washington, D.C, Hasbro Children's Hospital in Rhode Island, and Primary Children's Hospital in Utah. At each site, participants will be recruited at the time of UTI diagnosis from the emergency department (ED) and from a network of outpatient/private practice offices. Recruitment from the ED will be supervised by an ED physician (ED Enrollment Coordinator) and a part-time nurse.

III. Eligibility Criteria

Parents of febrile children 2 months (60 days) to 6 years of age (before sixth birthday) who have pyuria on urinalysis or dipstick and who do not meet any of the exclusion criteria will be asked to participate in the study (Table 2). We will exclude children younger than 2 months of age because, 1) the incidence of bacteremia is highest in this age group,^{22, 71} 2) clinical assessment of children <2 months of age is more difficult. Two studies in rats suggested that treatment of near-term premature animals with corticosteroids is associated with increased risk of adverse events; therefore, children between 2 and 3 months of age will only be enrolled if they are born at term (≥ 37 weeks).^{72, 73} We will limit the study to children with their first protocol defined UTI. This will minimize the number of children with preexisting scars secondary to previous UTIs. To minimize the number of children with false positive urinalyses, young children who have urine collected via a bag specimen for culture (without a follow-up

catheterized specimen) will be excluded. Other exclusion criteria are listed in Table 2. See last page of this document for changes made to the protocol after starting patient enrollment.

IV. Randomization

Subjects will be randomized in a 1:1 ratio. Randomization will occur in blocks of 4. Stratification will be based on the duration of fever (either documented or by touch) prior to diagnosis (<48 hours vs

≥ 48 hours) and the site of enrollment. That is, children will undergo site-specific blocked randomization sequences for each of the strata defined by duration of fever. Subjects are randomized into the appropriate strata based on this information. The investigator will be provided with a unique randomization code, which will

Table 3. Summary of Observations

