| Observation | Enrollment | Day 2- 4*** | 1 Month | Monthly | 5 - 24 mo |
|---|------------|-------------|---------|---------|-----------|
| Informed Consent | X | | | | |
| Detailed Medical History | X | | | | |
| DES* questionnaire | X | | | | |
| Constipation questionnaire | X | | | | |
| Randomization | X | | | | |
| Blood for biomarkers if parent consents | X | | | | |
| Urine biomarkers/creatinine | X | | | | |
| 1-month study visit/phone call | | | X | | |
| Phone call | | X | X | X | |
| Outcome DMSA** | | | | | X |

* Dysfunctional elimination questionnaire (for toilet trained children only)

** For children with reinfections, DMSA will be performed 4 mo. after last UTI

*** Until the fever has resolved

correspond to a code on one of the bottles of medication available at that site. In this way, only the central pharmacy will be aware of treatment assignment.

Any protocol defined recurrence will be treated with the same therapy initially given to the child. This treatment will be initiated as soon as possible after diagnosis (but no later than 48 hours of starting antibiotic therapy).

V. Data to be Collected (Table 3)

A. Baseline Data

Information on the following potential predictors and confounders of renal scarring will be collected during the baseline evaluation: Demographics (sex, race, ethnicity, age), symptoms (type and duration), past medical history (including result of prenatal ultrasound), medications [including non-steroidal anti-inflammatory drug use (NSAIDS)], and family history (VUR, UTI, scarring, kidney disease). There will be an age-appropriate evaluation for dysfunctional elimination syndrome (DES),⁷⁴ and constipation.⁷⁵ Blood, which will be optional if the parent is reluctant to have their child's blood drawn, and urine for all laboratory tests (Table 3) will be collected before steroids are administered and a portion of the specimen will be saved for future hypothesis-driven studies. If the parent consents to the genetic blood draw at the time of enrollment, this sample can be drawn at the time of the DMSA scan.

B. Follow-up

Day 2-4 Phone Call

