To monitor the child's wellbeing and to ensure compliance with medication administration, we will call parents for 3 days following the day of enrollment. If the child's fever has not resolved by day 4, we will continue daily phone calls until the child becomes afebrile. With recurrent UTI, the phone call sequence will begin the day after the study medication is administered and will end after the fever has resolved. At least two attempts each day will be made to contact a parent. Attempts should be made at different times of day or to more than one phone number, leaving a message to call us if there is no answer, with a 24-hour return phone number.

A positive urine culture will be defined as either a:

- 1) Urine specimen obtained by catheterization with:
 - a. The growth of one or more uropathogens at $\geq 50,000$ CFU/mL
 - OR
- 2) Urine specimen obtained by clean catch with:
 - a. The growth of one or more uropathogens at $\geq 100,000$ CFU/mL

For children who have a negative urine culture, corticosteroids will be stopped. All parents will be instructed to arrange a follow-up appointment with their primary care provider irrespective of culture results. Because of theoretical concerns regarding the anti-inflammatory effects of ibuprofen, parents will be asked to refrain from using ibuprofen (or other NSAIDs) during the study.²³

1-Month Visit (+/- 2 weeks)

Approximately one month after enrollment in the study, we will attempt meet parents of enrolled subjects to review 1) the results of the urine culture, 2) the results of any imaging tests ordered by the primary care provider as part of the management of the UTI, and 3) the plan for the remainder of the study period including a tour of the nuclear medicine department where the outcome DMSA will be performed. To save parents from making an extra trip, we will try to coordinate this visit with the routine imaging tests ordered by the child's PCP. If it is very difficult for parents to make this visit in person, we will conduct the visit over the phone.

The research nurse or the PI at each participating site will be available 24 hours a day to parents of enrolled children via a study-dedicated cellular phone or hospital-based beeper. Parents will be instructed to (1) contact

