of the kidney will be obtained, including posterior and posterior oblique projections using a high-resolution pinhole collimator 1.5 to 3 hours following injection. Scarring will be defined by the presence of cortical defects with or without loss of contours.^{76, 77} These cortical defects will be assessed semi-quantitatively by dividing the renal cortex into 12 equal segments (Table 4). The number of renal segments affected will be determined and the grade of scarring will be assigned based on a system developed by the Imaging Committee of the RIVUR study. DMSA scans will be interpreted by three reference radiologists without knowledge of clinical events or treatment arm. Inter-observer agreement will be assessed. To maximize reliability, we will request that each participating site send 10 de-identified DMSA scans (from children recently seen) to the reference radiologists for review prior to the start of enrollment. If the quality of the scans is suboptimal, appropriate changes will be made.

Table 4. Grading system for renal scarring

| Grade | Description |
|-------|---------------------------------|
| 1 | 1-2 kidney segments affected |
| 2 | 3-4 kidney segments affected |
| 3 | >4 kidney segments affected |
| 4 | Global atrophy/diffuse scarring |

E. Specimen Processing

Urine biomarkers – 1 mL of urine will be filtered, frozen, and processed in batches at CHP or the Luminex Facility at the Pittsburgh Cancer Institute. This method is well-established and is particularly suitable when the sample volume is limited. Concentrations will be measured using multiplex bead technology.

Blood biomarkers – At the time of UTI diagnosis, and if parents' consent to a blood draw, 1 mL of blood will be collected in EDTA plasma tubes for biomarker analysis.

VI. Statistical Analysis

Analysis plan– Efficacy of corticosteroids in the prevention of renal scarring

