The proportion of children who have any renal scars on the outcome DMSA scan in each treatment arm will serve as the principal outcome variable. Renal scarring will be defined as decreased uptake of tracer with or without loss of contours. We will also compare the proportion of children with severe scarring between groups. Severe scarring will be defined as the presence of grades 3 or 4 scarring on at least one kidney. Three reference radiologists, blinded to treatment assignment, will make all determinations and the reading endorsed by the majority will be used as the primary outcome measure. The analysis will follow intent to treat principles: subjects will be analyzed according to randomized treatment assignment regardless of adherence. Children who are found to have a negative urine culture will not be included in the efficacy analysis. These children do not have a UTI and are not at risk for developing renal scarring. Up to 6% of children (n=23) are expected to have a recurrent UTI in the follow-up period.²² It is estimated that for most of these children (~85%), the recurrent UTI episode will not result in renal scarring. As such, the effect of re-infections on the primary analysis will be minimal. The incidence and the extent of renal scarring in the two treatment groups will be compared using logistic regression. We will also test for statistical interaction for individual variables (age, gender, race, mother's education, fever duration, infecting organism, CRP, ibuprofen use within 24 hours of enrollment, and 5 preselected urinary biomarkers listed below) and steroid treatment. This is done to investigate the possibility that the relative treatment effect differs among patient subgroups. We are aware that tests for interaction generally have low statistical power and we will likely detect only marked differences in treatment effects in these subgroups. Furthermore, the additional problem of falsely identifying heterogeneity of treatment effect among patient subgroups in clinical trials is well known and therefore the interpretation of subgroup differences is considered exploratory and will be done with caution. Another analysis will be the proportion of children with recurrent febrile UTIs in each treatment group.

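### Does counting global atrophy as grade 4 scarring, with no rule for congenital dysplasia, undermine the scarring endpoints?

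*Combined protocol and SAP*

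**What the plan says.** Section C.VI makes any renal scar on the outcome DMSA scan the principal outcome, and reduced tracer uptake is enough to count. For the secondary comparison, "Severe scarring will be defined as the presence of grades 3 or 4 scarring on at least one kidney". Table 4 in section C.V.D describes grade 4 as "Global atrophy/diffuse scarring", without reference to origin. Three readers, blind to arm and clinical course, make the call, and the majority reading is used.

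Section B.I says of dysplasia that it "is characterized by globally atrophied kidney(s) with little or no function". It also says: "The clinical and radiological presentations of congenital and acquired scarring, albeit overlapping, are often distinct". In the primary-care studies it cites, "0% to 2% of children had evidence consistent with dysplasia at enrollment".

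The plan has partial safeguards:
- Section C.III states: "Other exclusion criteria are listed in Table 2". The body of that table is not in the text available for this review.
- Section C.V.A collects "past medical history (including result of prenatal ultrasound") among the possible predictors and confounders of scarring.
- The 1-month visit in section C.V.B reviews "the results of any imaging tests ordered by the primary care provider as part of the management of the UTI".
- Section C.V.C says all children will have the recommended imaging for their age and treats a normal ultrasound as reassurance against significant dysplasia. It also leaves routine imaging to the treating physician.

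Both the incidence and the extent of scarring are to be compared by logistic regression; no particular test is named.

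**The concern.** The feature that the background section treats as typical of congenital disease is scored as a treatment-preventable event in both the primary and the severe endpoint. Table 3 schedules no baseline scan, and the blinded readers cannot use the child's history. A kidney that was small from birth cannot respond to dexamethasone, so each one counted adds the same background to both arms and pulls the relative effect towards null. Severe scarring has fewer events, so the same handful of kidneys would weigh more there. The trial records prenatal and early imaging, yet no visible analysis uses it for this purpose.

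A second strand concerns the severe endpoint alone. With few events an arm could have none, and the Wald test from an ordinary logistic model then breaks down.

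**Working it through.** **Inputs.** From section C.VI: 15% scarring in controls, a 10-point difference (so 5% on treatment, risk ratio 1/3), two-sided 0.05, 80% power (the stated beta of 0.8 is read as power), 160 evaluable per arm, final level 0.048. From section B.I: dysplasia d between 0% and 2%. Assumptions: d is equal in the two arms, and every dysplastic kidney is read as a scar.

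**The plan's own figure.** Without continuity correction, n = [1.960·√(2·0.10·0.90) + 0.842·√(0.15·0.85 + 0.05·0.95)]² / 0.10² = 140.1, so 141 per arm. The continuity correction gives (140.1/4)·[1 + √(1 + 4/(140.1·0.10))]² = 159.5, so 160, which matches the plan. Inflation gives 160/(0.90·0.93) = 191.2 against 190 stated, and 160/(0.90·0.70) = 254.0 against 260 stated. Both are close.

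**Number affected.** 0.02 × 320 = 6.4 children at the upper bound, and none at the lower.

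**Primary power.** Exact binomial enumeration, 160 per arm, score test at 0.048. If dysplasia adds to the acquired rates, each arm's rate is d + (1 − d)·p. If it already sits inside the 15%, controls stay at 15% and the treated rate is d + (0.15 − d)/3.

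| d | Adds: rates | Power | Inside: rates | Power |
|---|---|---|---|---|
| 0% | 15% vs 5% | 86.4% | 15% vs 5% | 86.4% |
| 1% | 15.85% vs 5.95% | 82.4% | 15% vs 5.67% | 79.7% |
| 2% | 16.7% vs 6.9% | 78.5% | 15% vs 6.33% | 71.8% |

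At 2% the absolute difference shrinks from 10 points to 9.8 or 8.7. A continuity-corrected normal approximation at 0.05 starts lower: 80.1% at d = 0, then 76.2% or 72.8% at 1%, and 72.3% or 64.6% at 2%. The usual tests from a logistic model carry no such correction, so the table is the closer guide.

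**What a sensitivity analysis could recover at d = 2%.** If half of the dysplastic kidneys were identified and not counted, its power would be 82.4% (adds) or 76.6% (inside); if all were, 86.4% or 81.5%. These figures describe the extra analysis. The primary test keeps the power in the table.

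**Severe scarring.** The document gives no rate, so take 3% acquired in controls and a risk ratio of 1/3 as an assumption. At d = 2% the rates are 0.02 + 0.98·0.03 = 4.94% and 0.02 + 0.98·0.01 = 2.98%. The risk ratio moves from 0.33 to 0.60, while the difference moves only from 2.00 to 1.96 points. With an assumed 1% or 5% in controls the risk ratio becomes 0.78 or 0.53.

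Without any dysplasia, 3% vs 1% has 23% power by the score test at 0.05 and 5% by the Wald test. The chance of at least one empty arm is 1 − (1 − 0.97¹⁶⁰)(1 − 0.99¹⁶⁰) = 1 − 0.992·0.800 = 0.206. Low power here comes from the rarity of the event, with or without dysplasia.

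**The case for a change.** The case for acting is that the gap is real and cheap to close. An exclusion in Table 2 could remove only known cases, and dysplasia unrecognised at a first UTI visit would still be enrolled. At 2%, power falls below 80% under either reading. The data are mostly collected already, and a blinded classification fixed before unblinding is more credible than one devised after a borderline result.

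The facts in this stand: the visible text has no rule, and the arithmetic is right. The remedy is weaker than it looks, for three reasons.

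- Keeping the endpoints as defined, which is sensible, leaves the described power loss where it was.
- Apart from the prenatal ultrasound, the usual source would be imaging up to the 1-month visit, which can fall six weeks after enrollment and so well after the 3-day course. If treatment prevents early shrinkage, more control kidneys than treated ones could be set aside as congenital. That would turn balanced misclassification into a difference between arms.
- Imaging is partly discretionary, so not every child could be classified. A child with both kidneys affected would have no other kidney to score.

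On the severe endpoint, the point about empty arms is correct for a Wald test, but the plan names no Wald test. The score test is itself a logistic-regression test.

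**Conclusion.** No change is needed. The missing rule leaves a balanced misclassification of 0 to about 6 of 320 children. It does not raise the type I error, and at 0% it has no effect. At 1% dysplasia primary power stays at about the planned 80% (82.4% or 79.7%). At 2% it is 78.5% or 71.8%, so only the upper bound combined with dysplasia already inside the 15% gives a clear shortfall.

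Those losses are upper limits of a kind. They assume that every dysplastic kidney is read as a scar, although the document calls the two presentations often distinct. They also carry the prevalence over from other studies without allowing for this trial's exclusions. Whether the 15% already includes dysplasia cannot be settled from the text: section B.I reports the two separately, but the design rate comes from a meta-analysis whose content is not given.

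Scoring what the blinded readers see, without judging its origin, is a fair trade-off. It keeps the outcome free of clinical information, at the price of slight dilution. The prenatal ultrasound result is already recorded, so analysts can look at any grade 4 kidneys against it without altering the plan. The choice of test for rare severe events is a detail that an analyst facing an empty arm would handle sensibly, and the severe-scarring rates used to make it look serious are assumptions.

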Data will be analyzed after approximately one third of enrolled children complete the outcome DMSA scan. If there is a significant difference between groups, the DSMB may consider the possibility of terminating the study. Type I error will be controlled by using the method of Fleming, Harrington and O'Brien. Testing will be conducted at significance levels of 0.005 and 0.048 at the interim and final analysis, respectively.⁷⁸

We will also compare the mean proportion of scarring in the two treatment groups across the three radiologists while adjusting for the correlation resulting because the radiologists evaluated the same set of scans.

Because some of the STARRs participants also participated in the companion “Biomarkers for Pyelonephritis” study, in which early DMSA scan is performed to determine whether pyelonephritis is present, we will examine the efficacy of treatment in children with and without pyelonephritis.

The study will be powered to detect a 10% difference between the two arms. A 10% absolute difference between the two groups translates into a number needed to treat of 10 (i.e., 10 children will need to be treated to prevent one child from developing scars). Assuming a 15% rate of scarring in the control group, a two-sided alpha of 0.05, a beta of 0.8, a 10% attrition rate, and a 7% rate of false positive urinalysis, 190 children will be required per group (i.e., 160 evaluable children per group). However, as the study progressed, we realized that 30% of children enrolled had a false positive urinalysis, and thus increased the required sample size to 260 children per group (to arrive at the 160 evaluable children needed). The 15% rate of scarring in the control group comes from a meta-analysis we conducted.⁷⁹ The attrition rate is based on our previous study of intravenous versus oral antibiotics for the treatment of UTI which was also a randomized multicenter study with a 6-month follow-up DMSA.²²

A recent study described several urinary biomarkers that appear promising in differentiating children with pyelonephritis from children with cystitis.⁸⁰ Because only children with pyelonephritis are at risk for renal scarring, these markers could potentially be used to select children for treatment with adjuvant corticosteroids. As such we will examine for interactions between 5 such biomarkers and treatment effect. Logistic regression

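### The primary logistic regression names no baseline covariate, although candidate predictors of scarring are scheduled at enrolment; fixing two in advance would be a cheap, modest efficiency gain

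*Combined protocol and SAP*

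**What the plan says.** Section C.VI defines the primary endpoint: "The proportion of children who have any renal scars on the outcome DMSA scan in each treatment arm will serve as the principal outcome variable". The method is one sentence: "The incidence and the extent of renal scarring in the two treatment groups will be compared using logistic regression". No covariate is listed. The text does not call the model unadjusted either.

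Section C.V.A (Baseline Data) introduces its list of items with: "Information on the following potential predictors and confounders of renal scarring will be collected during the baseline evaluation". Table 3 schedules urine markers at enrolment without qualification, and C.V.A has the samples taken before steroids. Blood is optional, and the elimination questionnaire is for toilet-trained children only.

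C.VI then gives the baseline variables one named use: treatment-by-variable interaction tests, with subgroup differences treated as exploratory. The five urinary markers (IL-15, MCP1, CXCL1, interferon gamma, NGAL) are justified this way: "Because only children with pyelonephritis are at risk for renal scarring". The only mention of adjustment belongs to those marker interaction models.

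On design: "The study will be powered to detect a 10% difference between the two arms". The inputs are: "Assuming a 15% rate of scarring in the control group, a two-sided alpha of 0.05, a beta of 0.8" (the last figure is evidently power). They give 160 evaluable children per group. On error control: "Testing will be conducted at significance levels of 0.005 and 0.048 at the interim and final analysis, respectively".

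**The concern.** If the plan's reasoning is right, some analysed children can scar and others cannot, and a measurement taken before dosing carries information on which is which. With few events, a chance imbalance in at-risk children between the arms adds noise to the comparison. Adjusting for a prognostic baseline value removes part of that noise at the same sample size. Using these values only in interaction models forgoes that benefit.

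The silence has a second consequence. With no covariate set stated, the model behind the primary result could be chosen after the data are seen.

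**Working it through.** **1. The plan's own figure.** Take p1 = 0.15, p2 = 0.05, mean 0.10, two-sided alpha 0.05 and power 0.80.

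n = [1.960·√(2·0.10·0.90) + 0.842·√(0.15·0.85 + 0.05·0.95)]² / 0.10² = (0.8315 + 0.3521)² / 0.01 ≈ 140.1, so 141 per group.

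With continuity correction: (140.1/4)·[1 + √(1 + 4/(140.1·0.10))]² ≈ 159.5, so 160. The stated 160 is reproduced.

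**2. Unadjusted power at the final level of 0.048.** Φ[(0.10·√160 − 1.977·0.4243)/0.4183] = Φ(1.018) ≈ 0.846. Simulated likelihood-ratio tests give about 0.86 to 0.87. Both exceed 0.80.

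**3. Events.** 160·0.15 + 160·0.05 = 24 + 8 = 32 at the final analysis. If the interim takes one third of the 320 evaluable children, that is about 107 children and 107·0.10 ≈ 11 scars. If one third of all 520 enrolled is meant, it is about 173 children and 17 scars.

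**4. What the documents' figures allow for a pyelonephritis marker.** Section B.II puts renal involvement at about two-thirds. C.VI places all scarring risk there, so scarring among those children is 0.15/(2/3) = 22.5% versus 0.05/(2/3) = 7.5%.
- A perfect marker amounts to analysing 160·2/3 ≈ 106.7 per arm at 22.5% versus 7.5%. Power is Φ[(0.15·√106.7 − 1.977·0.5050)/0.4937] = Φ(1.115) ≈ 0.868, against 0.846. The gain is about 2 points.
- In the control arm its AUC for scarring is 0.333/0.85 + 0.5·(1 − 0.333/0.85) = 0.392 + 0.304 = 0.696.
- An imperfect marker was simulated in a model with age (assumed non-prognostic), the marker, 10% missing values (assumed), mean fill and a missing indicator; 4,000 trials per case:

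| Assumed marker AUC for pyelonephritis | Unadjusted power | Adjusted power |
|---|---|---|
| 0.75 | 0.871 | 0.870 |
| 0.85 | 0.855 | 0.865 |
| 0.95 | 0.866 | 0.873 |

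**5. If baseline values grade the risk of scarring itself.** Same model and missingness, 15% versus 5%, level 0.048:

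| Assumed AUC for scarring | Unadjusted power | Adjusted power | Gain (points) |
|---|---|---|---|
| 0.70 | 0.866 | 0.880 | 1.4 |
| 0.75 | 0.876 | 0.899 | 2.3 |
| 0.80 | 0.866 | 0.905 | 3.9 |

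**6. Type I error.** At the final analysis the adjusted test ran at 0.047 to 0.054. In separate null runs with a single complete predictor, the unadjusted test ran at 0.051 to 0.054 and the adjusted one at 0.053 to 0.055, so the slight excess over 0.048 is not caused by adjustment. At the interim size the adjusted test ran at about 0.007 against 0.004 unadjusted, nominal 0.005. In another run with 106 children it was 0.0079 against 0.0047 at 15% scarring, and 0.008 for both at 10%.

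**7. Too many terms.** Adding five uninformative covariates cost up to about 0.5 point of power and took null rejection to 0.054 to 0.058.

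**The case against.** The strongest case against runs as follows.

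- **Silence is not exclusion.** A reader might infer that the plan deliberately leaves every predictor out of the primary model. The text does not say so; the covariate set is unspecified. This stands. It also supports naming the set, since an open choice can be settled after unblinding.
- **Not every predictor is available in every child.** A reader might infer complete collection. Optional blood and the restricted questionnaire rule that out for the whole list. Age and urine are scheduled for all, which is why the fix uses only those.
- **The larger gains need more than the documents claim.** The markers are credited only with telling pyelonephritis from cystitis, and even a perfect one reaches an AUC of about 0.70 for scarring. Values of 0.75 to 0.80 require grading of risk within pyelonephritis, or another strong predictor. This stands, and the size is stated accordingly.
- **No composite score exists.** C.VI lists five separate markers with no rule for combining them. This stands; one named marker is the simpler choice.
- **The interim is too sparse.** This stands for the adjusted test. The unadjusted likelihood-ratio test was not exact in every sparse setting either.
- **The randomisation factors are not named either.** True, but six sites need five terms, which is heavy for 32 events. It is a separate decision.
- **An unadjusted comparison of randomised arms is valid and matches the 10-point target.** This stands, so adjustment is a matter of efficiency.

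**Conclusion.** The point holds in a limited form. The plan pre-specifies no baseline covariate for its primary model, although it schedules measurements that it expects to be informative. Naming a short set in advance would gain about 0 to 1 point of power if the marker only separates pyelonephritis from cystitis (about 2 by formula for a perfect marker), and about 1 to 4 points if baseline values predict scarring with AUC 0.70 to 0.80. Those AUCs are assumptions, as are the 10% missingness and the non-prognostic age. No simulated case lost power beyond simulation noise.

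A reader might infer that the trial is underpowered or its primary test flawed. The documents do not support that: 160 per arm reproduces, and unadjusted power is about 85 to 87% against a target of 80%. This is a cheap improvement in efficiency and pre-specification.

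**What to change.** In C.VI, before unblinding:

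1. State that the final primary logistic model includes as main effects age (continuous) and one named, log-transformed urinary marker from the five preselected. A composite is acceptable if its formula is fixed without using outcome data by arm.
2. Fill a missing marker value with the mean and add a missing indicator.
3. Test treatment by likelihood ratio at 0.048.
4. Standardise the fitted model to report the scarring proportion in each arm and their difference, to match the 10-point target.
5. Keep the unadjusted comparison as a sensitivity analysis.
6. Keep the 0.005 interim test unadjusted.

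The cost is plan wording and a few lines of code; no new data are needed. The downsides are that the odds ratio becomes conditional, hence the standardised proportions, and that about 32 events limit the model to two or three prognostic terms.
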